12.5 Post study drug supply

The Sponsor will not provide vorapaxar to study participants beyond the duration of the study.

13.0 Biological samples

13.1 Blood collection

It is important that the handling of blood samples is undertaken according to local guidelines and regulations for handling infectious substances. The blood tubes required to be used for each test should be as per local laboratory guidelines. Storage samples will be collected for d-dimer, IL-6 and Hs-CRP analysis at a central laboratory as well as other exploratory analyses. This includes plasma, serum and PBMC. The blood tubes required for storage samples will be outlined in the MOOP. These samples will be processed locally and then shipped to central laboratories for storage and analysis.

Any unused plasma, serum or PBMC samples (unused back up samples or if exploratory analyses are not conducted due to failure to reach the primary endpoint) will be kept for possible future HIV related research.

Ethics approval would need to be granted for any future HIV research on these samples prior to these samples being released.

The following details can be found in the laboratory MOOP:

- Types and quantities of specimens
- Collection schedule
- Methods for processing laboratory samples prior to analysis
- Shipping and storage

Only the laboratory supplies as described in the clinical trial agreement with sites are to be provided by the Sponsor. It is strongly recommended that the blood is collected on the date of the actual study visit. However, if this cannot occur for some particular reason, a blood sample taken within 2-3 days of the actual visit date is acceptable. However, all blood samples for eligibility purposes must be taken at the screening visit.

13.2 Labelling of blood collection tubes

Blood collection tubes should be labelled accurately and legibly as outlined in the MOOP. The Sponsor can provide the site with specimen labels if needed. These labels are only to be used on the blood tubes to be sent to the local laboratory, not to be placed on the aliquot tubes for frozen storage. Aliquot tubes for storage must only be labelled with the participant's identification number.

13.3 Transportation of samples

It is important that during the transportation of blood samples precaution is taken according to local guidelines and regulations for handling infectious substances.

Sites will be required to set up the procedures for transporting the blood tubes to the local laboratory. It is important that the samples arrive at the laboratory within 3 hours of blood collection (this time frame is determined by need to process the plasma sample for d-dimer within 4 hours of collection).

It is the responsibility of the Principal Investigator at each site to ensure that all site staff handling, packaging, and/or shipping biological samples understand and comply with International Air Transport Association (IATA) regulations relating to the handling and shipping of hazardous goods and/or diagnostic specimens. Methods for packaging and shipping biological samples are detailed in the laboratory MOOP.

13.4 Storage of samples

Plasma, serum and PBMC samples will be collected and processed at the local laboratory. The samples will be stored in the interim at local laboratories and then sent for central storage at St Vincent's Centre for Applied Medical Research laboratory (AMR) in Sydney at regular intervals throughout the study. Transport to AMR in Sydney will be organised by The Kirby Institute. The cost of processing and storage of bloods will be provided to the sites as per the clinical trial agreement. For more detailed information on the types of tubes and processing requirements please refer to the Manual of Operations.

13.5 Processing of samples

All blood samples for routine clinical care and safety monitoring will be analysed at the local laboratory. Analysis of d-dimer, IL-6 and Hs-CRP will be performed centrally at LEIDOS Biomedical Research Inc. in the USA on frozen plasma samples from each participant.

It is important that the handling of blood samples is undertaken according to local guidelines and regulations for handling infectious substances. The investigator may be contacted should the technical condition of the sample, absence of information or inconsistencies on the request form be such that the samples cannot be processed. Demographic errors (i.e. incomplete or inconsistent participant information) will be called through to the site and a faxed confirmation of correct information requested. Where such errors are noted after a report has been sent to the site, then a second corrected report will be reissued by the local laboratory.

13.6 Reporting of results

The blood results from routine clinical care and safety monitoring will be reported to the site as per local standard procedure. It is important that once these results are received they are entered into the eCRF and a hardcopy of the results are kept in the medical notes. If results are received electronically, the electronic format is adequate for source data verification.

13.7 Plasma d-dimer determination

Plasma d-dimer will be measured at the local laboratory for assessment of eligibility. Plasma samples at weeks 0, 1, 4, 8, 12 and 18 will be stored and sent to a central laboratory (LEIDOS Biomedical Research Inc. in the USA) for central assessment of d-dimer, IL-6 and Hs-CRP at the end of the study. These central results will be used for the analysis of the study. Results cannot be provided in real time to individual patients. Results will be provided at completion of the project.

14.0 Data collection, source documents and record retention

14.1 Records and reports

The Principal Investigator or designee is responsible for preparing and maintaining adequate and accurate case histories designed to record all observations and other data pertinent to the investigation on each individual treated with the investigational product. Data reported on the CRF that are derived from source documents must be consistent with the source documents or the discrepancies must be explained.

14.2 Source documents

Source documents include all recordings of observations or notations of clinical activities and all reports and records necessary for the evaluation and reconstruction of the study. Source documents include, but are not limited to, participant medical records, laboratory reports, ECG tracings, X-rays, radiologist reports, biopsy reports, ultrasound photographs, participant progress notes, pharmacy records and any other similar reports or records of procedures performed in accordance with the protocol. It is not acceptable for the CRF to be the only record of the participant's study participation and progress as these must also be recorded in the participant medical record. This is to ensure that anyone accessing the participant's medical record has adequate knowledge of their participation in a clinical study.

Any document that acts as a source document (the point of the initial recording of a piece of data) should be signed and dated by the person recording or reviewing the data for issues of medical significance (for example the review of laboratory reports). Persons signing the source documents must be listed, on the appropriate study documentation (site delegation log), as a site staff member.

14.3 Submission of data

Data will be collected for this study using an Electronic Data Capture system using a web-enabled password protected platform. Following each participant visit the designated site staff will complete the visit specific eCRF. The Principal Investigator is responsible for ensuring the data collected are complete, accurate and recorded in a timely manner. The confidentiality of records that could identify participants must be protected, respecting the privacy and confidentiality rules in accordance with the applicable regulatory requirement(s).

Once all of the information is received the eCRF will be completed. Sponsor staff will then monitor the data for completeness and accuracy. Any discrepancies either manual or automatic will be notified to the site staff for clarification. Corrections to eCRFs will only be possible by study personnel with sufficient authorisation to make changes. All changes will record time, date, computer ID and the name of the authorised person's access code.

14.4 Records retention and archiving

The Investigator must retain investigational product disposition records, copies of CRFs (or electronic files) and source documents for the maximum period required by applicable regulations and guidelines, or Institution procedures, or for 15 years, whichever is longer. The Investigator must contact the Sponsor prior to destroying any records associated with the study.

If a Principal Investigator withdraws from the study (e.g. relocation, retirement), the records will be transferred to a mutually agreed-upon designee or site (i.e. another Investigator or IRB). Notice of such transfer will be given in writing to the Sponsor.

14.5 Study monitoring

Representatives of the Kirby Institute or NIAID must be allowed to visit all study site locations periodically to assess the data, quality and study integrity. On site, Kirby Institute or NIAID representatives will review study records to directly compare them with source documents, discuss the conduct of the study with the Principal Investigator or their designee and verify that the facilities remain acceptable.

Monitoring visits will be scheduled in advance and with sufficient warning to allow arrangements of diaries and personnel as appropriate. The number of visits shall depend upon recruitment rate; however, the monitor shall conduct a minimum of two source data verification visits at each site during the study. These shall occur shortly after the study entry of the first participant(s) and at the end of the study once all study visits have been completed.

The Principal Investigator is responsible for retaining all essential documents listed in ICH Good Clinical Practice (GCP) guidelines. These must be organised in a comprehensive filing system that is accessible to study monitors and other relevant personnel.

14.6 Auditing

The study may be subject to audit by the Kirby Institute, NIAID, Merck, the ethics committee, relevant regulatory agencies or the relevant government authorities. Under such circumstances, the investigator must agree to allow access to study documents and relevant hospital/clinic records. Audit reports will be kept confidential between the site and the Sponsor.

The Principal Investigator must notify the Sponsor promptly of any inspections scheduled by regulatory authorities and forward copies of inspection reports to the Sponsor.

15.0 Ethics committee/regulatory approval and informed consent

15.1 Ethical conduct of the study

This study shall be conducted in accordance with the ethical principles laid out in the National Statement on Ethical Conduct in Research Involving Humans, the Declaration of Helsinki (most current version issued, available at www.wma.net) and will be consistent with GCP, and applicable regulatory requirements.

The rights, safety and wellbeing of the study participants are the most important considerations and should prevail over interests of science and society. All personnel involved in conducting this study will be qualified by education, training, and experience to perform their respective task(s).

The Sponsor is responsible for obtaining regulatory approval for the study. Before study initiation, the Investigator must have written and dated approval/favourable opinion from the IRB/IEC and local regulatory authorities for the protocol, consent form, participant recruitment materials/process (e.g. advertisements) and any other written information to be provided to participants. The approval must clearly identify all documents approved by the IRB/EC and regulatory authorities including version number and dates of the protocol and participant information/informed consent form. A copy of the approval must be sent to the study Sponsor.

The Principal Investigator must comply with all IRB/EC, and where relevant regulatory authorities, reporting requirements for all serious or unexpected AEs, annual updates and end of study reports and must agree to abide by any IRB/EC conditions of approval. Researchers must inform the IRB/IEC, and where relevant regulatory authorities, as soon as possible of any new information from other published or unpublished studies which may have an impact on the continued ethical acceptability of the study or which may indicate the need for amendments to the study protocol. In addition, the Principal Investigator should provide any updates or other information required by relevant parties in accordance with any local regulatory requirements or institution procedures.

This study will not use the services of study personnel where sanctions have been invoked or where there has been scientific misconduct or fraud (e.g. loss of medical licensure, debarment).

Monitoring systems with procedures to maximise the quality of every aspect of the study will be implemented.

15.2 Compliance with the protocol and protocol revisions

The study shall be conducted as described in this approved protocol. The protocol and any amendments and the participant information and consent will receive IRB/IEC approval prior to initiation of the study. This

study will be reviewed by the relevant local ethics committees and regulatory authorities, in accordance with current local guidelines. The Sponsor will assist in the process of approval as required by each individual site.

The Principal Investigator should not implement any deviation or change to the protocol without prior review and documented approval/favourable opinion from the IRB/IEC of an Amendment, except where necessary to eliminate an immediate hazard(s) to study participants. Any significant deviation must be documented and notified to the Sponsor.

If a deviation or change to a protocol is implemented to eliminate an immediate hazard(s) prior to obtaining IRB/IEC approval/favourable opinion, as soon as possible the deviation or change will be submitted to:

- IRB/IEC for review and approval/favourable opinion;
- The Sponsor;
- Regulatory Authority(ies), if required by local regulations.

Documentation of approval signed by the chairperson or designee of the IRB/IEC must be sent to the Sponsor along with other required documentation.

If the revision is an Administrative Letter, the Principal Investigator must inform their IRB/IEC.

If an Amendment substantially alters the study design or increases the potential risk to the participant: (1) the consent form must be revised and submitted to the IRB/IEC for review and approval/favourable opinion; (2) the revised approved form must be used to obtain consent from participants currently enrolled in the study if they are affected by the Amendment; and (3) the new approved form must be used to obtain consent from new participants prior to enrolment.

Preparation of the consent form is the responsibility of the Principal Investigator and must include all elements required by ICH-GCP and applicable regulatory requirements, and must adhere to GCP and to the ethical principles that have their origin in the Declaration of Helsinki. The consent form must also include a statement that the sponsor, Merck, the ethics committee, and regulatory authorities will have direct access to participant study records (See Appendix 5 for participant information and consent form template).

Prior to beginning the study, the Principal Investigator must have the IRB/IEC's written approval/favourable opinion of the written informed consent form and any other information to be provided to the participants.

The Principal Investigator should endeavour to provide the participant or legally authorised representative with a copy of the consent form and written information about the study in the language in which the participant is most proficient. The language must be non-technical and easily understood. The Principal Investigator should allow time necessary for participant or participant's legally authorised representative to inquire about the details of the study. The Principal Investigator must ensure that participants or their legally authorised representative are clearly and fully informed about the purpose, potential risks and other critical issues regarding clinical trials in which they volunteer to participate.

Freely given written informed consent must be obtained from every participant or his or her legally authorised representative prior to any protocol-specific procedures being conducted on that participant. Consent must be documented by the participant's dated signature on a consent form along with the dated signature of the person conducting the consent discussion.

If the participant is illiterate, an impartial witness should be present during the entire consent discussion. Once the discussion is complete, the participant must sign and date the informed consent form, if capable.

The impartial witness must also sign and date the informed consent form along with the person who conducted the consent discussion.

Should an ethics committee-approved informed consent form not be available in a participant's most proficient language, then a translator should be sought. This translator should act as a witness to the informed consent process and be asked to sign the informed consent form accordingly.

If the participant is legally incompetent (i.e. mentally incapacitated) the written consent of a parent, guardian or legally authorised representative must be obtained.

Imprisonment or the compulsory detention for treatment of either a psychiatric or physical (e.g. infectious disease) illness precludes enrolment in clinical trials.

When a participant may be in a dependent relationship with the investigator, a well-informed physician who is not engaged in the study and is completely independent of the relationship between the participant and investigator should obtain the participant's informed consent. This issue will be addressed within the site training process.

The participant or legally authorised representative should receive a copy of the signed and dated informed consent and any other written information provided prior to the participant's participation in the study.

15.4 Updates to the consent form

The informed consent and any other information provided to participants or the participant's legally authorised representative, should be revised whenever important new information becomes available that is relevant to the participant's consent. This information should receive IRB/IEC approval/favourable opinion prior to use, except if the safety of the participant is compromised. The Principal Investigator, or a person designated by the Principal Investigator, should fully inform the participant or the participant's legally authorised representative of all pertinent aspects of the study and of any new information relevant to the participant's willingness to continue participation in the study. This communication should be documented. During participation in the study, any updates to the consent form and/or the written information will be provided to the participant.

16.0 Confidentiality of data

16.1 Confidentiality of participant records

By signing the Clinical Trial Agreement, the site Principal Investigator agrees that the sponsor, IRB/EC or regulatory authorities may consult and/or copy study documents to verify information in the case report form. By signing the consent form the participant agrees to these processes.

Participant confidentiality will be maintained at all times and no documents containing the participant's name or other identifying information will be collected by the sponsor. It may be necessary for the sponsor's representatives, the IRB/EC and regulatory authority representatives to have direct access to the participant's medical records. If study documents need to be photocopied during the process of verifying case report form data, the participant will be identified by a unique code only; full names and other identifying information will be masked.

16.2 Confidentiality of study data

By signing the Clinical Trial Agreement, the site Principal Investigator affirms to the sponsor that information provided to them by the sponsor will be maintained in confidence and divulged only as necessary to the ethics committee and institution employees directly involved in the study. Both ethics committee members and employees must also understand the confidentiality requirements for any information divulged to them. The data generated by this study will be considered confidential, except where it is included in a publication as agreed in the publication policy of this protocol.

17.0 Governance

This international research protocol is funded by The National Health Medical & Research Council, Australia. The study intervention/clinical trial supplies will be provided by Merck. The study is sponsored by the University of New South Wales (UNSW) and coordinated through the Kirby Institute for infection and immunity in society. The Kirby Institute has established governance and implementation structures which use resources efficiently to deliver program objectives on schedule.

17.1 Protocol Steering Committee (PSC)

There will be a single PSC chaired by [name]. This group will comprise a representative from each participating site, representatives from UNSW and NIAID project teams and the project biostatistician. A representative from Merck will also be invited to join the PSC. The PSC will seek the expertise of other key opinion leaders as necessary. The PSC will be the primary management entity for the collaborative study group. This group will meet by teleconference, arranged as required and at least twice per year during the study follow up period. Decisions in this group will be reached by consensus among the designated membership. Routinely the views of other stakeholders will be sought at meetings of the PSC and this will allow others to attend meetings. The PSC, comprised of members from a range of internal and external stakeholders will guide the design, implementation and conduct of the study.

17.2 Project Team

Day-to-day management of the protocol will be undertaken by a dedicated project team based at The Kirby Institute at UNSW and NIAID and supported as required by contract service organisations. The Project Team is accountable to the PSC.

For contact details on the clinical trial sites, laboratories and pharmacies please refer to the MOOP.

18.0 Data Safety and Monitoring Board (DSMB)

The DSMB will be accountable to the PSC and will undertake independent review of protocol-specified and ad hoc interim analyses if required. The DSMB will be composed of individuals neither directly associated with the study nor employees of any of the organisations responsible for the conduct of the research. The study biostatistician will be an ex officio member of the DSMB. The primary focus of the reviews undertaken by the DSMB will be safety. The first scheduled review will take place after 20 patients have completed 6 weeks of treatment with further reviews scheduled every 8 weeks thereafter. For ad hoc reviews an interim analysis would be prompted when four (4) BARC type 2 events or one (1) BARC type 3 event are reported. During the ad hoc review and until the PSC has received and acted upon a DSMB recommendation, patient recruitment will be paused but randomised patients will continue study treatment. The terms of reference and operating

guidelines of the DSMB will be drafted by the study biostatistician (as documents separate to the Protocol) and finalised in collaboration with the DSMB prior to the commencement of the study.

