3.3 Vorapaxar

Vorapaxar sulphate (Zontivity™) is a first in class, tricyclic himbacine-derived selective inhibitor of platelet aggregation mediated by PAR-1.

Vorapaxar has been developed in a number of primary and secondary care settings for cardiovascular diseases. In the setting of acute coronary syndromes vorapaxar did not affect a composite primary endpoint that included death, MI, stroke, recurrent ischemia or coronary revascularisation but did significantly

increase the risk of major bleeding including intracranial haemorrhage¹¹. In a further study that followed 26,449 patients with a history of MI, cerebral stroke or peripheral arterial disease, vorapaxar significantly reduced the risk of cardiovascular disease mortality and ischemic events among patients with stable atherosclerosis while also increasing the risk of moderate to severe bleeding including intracranial haemorrhage¹². This study identified the risk of severe bleeding among patients with a history of stroke – which would now be regarded as contraindicated for treatment with vorapaxar and therefore participation in this study. Importantly, the findings arose among a patient group who were also receiving standard secondary prophylaxis for CVD (88% receiving aspirin and 78% receiving thienopyridine) and so the effects reflect adjunctive use to already potent anti-thrombotic therapy. The hazard ratio (95% CI) for vorapaxar recipients relative to placebo recipients for the primary endpoint (fatal CV event, MI or stroke) was 0.87 (0.80-0.94; $p < 0.001$). A total of 2204 patients experienced a primary event over three years, 1028 (9.3%) vorapaxar recipients and 1176 (10.5%) of placebo recipients. Moderate or severe bleeding occurred in 4.2% of patients who received vorapaxar and 2.5% of patients who received placebo (HR, 1.66; 95% CI 1.43–1.93; $p < 0.001$).

Vorapaxar has now been licensed in the USA as secondary prophylaxis for patients with a history of MI or peripheral arterial disease except ischemic stroke.

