10.3.2.3 BARC Type 3 Bleeding

Participants who develop a BARC type 3a, 3b or 3c (intracranial or intraocular) bleeding event will have the study drug permanently discontinued. Participants experiencing BARC type 3a or 3b AEs must be followed regularly (at least 4-5 times per week is suggested) until resolution of the adverse event. Participants experiencing a BARC Type 3c event (intracranial or intraocular bleed) must be followed on a daily basis until the resolution of the event. The patient should remain on study and continue to undergo protocol-specified evaluations and assessments. A BARC type 3 event would trigger an 'out of session' meeting of the Data Safety Monitoring Board to review the event in an unblinded manner.

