10.3.2.4 BARC Type 4 Bleeding

Any participant who is planning to undergo any planned surgical procedure 6 months after the planned randomisation should not be enrolled into the study. If there is a need for a participant to undergo an emergency CABG or any other surgical procedure during the course of the study, the study drug should be immediately and permanently discontinued. If deemed necessary, unblinding procedures could be initiated but attention to how best do this will be given to avoid site staff becoming aware of the treatment allocation.

It is important that the treating physician is informed that vorapaxar results in residual platelet aggregation activity 4 weeks after stopping and appropriate clinical decisions are made. There is no known antidote for vorapaxar. It is the investigator’s responsibility to inform the treating physician of this.

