10.3.2.5 BARC Type 5 Bleeding

If any participant suffers a fatal bleed the blind for that participant will be broken. If the participant was taking vorapaxar at the time of the event, the trial will be temporarily stopped whilst the Data Safety Monitoring Board (DSMB) reviews the event in light of other clinical safety information for the study. Please see section 18.0 for details on DSMB.

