10.4 Discontinuation of study treatment

In general terms, all randomised study participants should aim to take the study treatment as per protocol. However, reasons for either temporarily or permanently ceasing study treatment include:

- Disease progression requiring medical intervention
- Surgical intervention
- Administration of prohibited therapy
- Investigator or participant wish to stop therapy
- Occurrence of unacceptable adverse drug reactions

Participants MUST be discontinued from study treatment if there is any clinical adverse event, laboratory abnormality or intercurrent illness that in the opinion of the investigator indicates that continued treatment with study therapy is not in the best interest of the participant.

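### After an ad hoc safety trigger, Protocol section 18.0 keeps participants without a stopping event on study drug until the PSC acts, even if the DSMB recommends a hold or stop

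*Protocol*

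**What the plan says.** Protocol section 18.0 makes the DSMB accountable to the PSC. It sets two triggers for an ad hoc review: four BARC type 2 events or one type 3 event. During that review and afterwards, "until the PSC has received and acted upon a DSMB recommendation, patient recruitment will be paused but randomised patients will continue study treatment". The sentence draws no distinction by the content of the recommendation.

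Section 17.1 describes how the PSC works: "This group will meet by teleconference, arranged as required and at least twice per year during the study follow up period". It decides by consensus. Neither 17.1 nor 18.0 gives a time within which it must respond to the DSMB. The SAP has no text on the DSMB or on stopping.

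Other sections stop drug in particular cases:

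- 10.3.2.3: permanent discontinuation for the participant with a type 3 bleed, and a "meeting of the Data Safety Monitoring Board to review the event in an unblinded manner".
- 10.3.2.2: discontinuation for a type 2 bleed that needs medical intervention or leads to hospitalisation or increased care.
- 10.2 and 10.4: dosing ceases where vorapaxar is suspected in a significant adverse event, and must stop where the investigator judges, after an event, laboratory abnormality or illness, that continuing is not in the participant's interest. Section 10.4 also lists "Investigator or participant wish to stop therapy" as a reason to stop.
- 10.3.2.5: after a fatal bleed on vorapaxar, "the trial will be temporarily stopped whilst the Data Safety Monitoring Board (DSMB) reviews the event".
- 15.2: an investigator may deviate without prior ethics approval "except where necessary to eliminate an immediate hazard(s) to study participants".

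**The concern.** An ad hoc review exists mainly to protect the participants who have not yet bled. If the independent board concludes that dosing should be held, section 18.0 as written tells sites to keep treating those participants until a second committee has met and agreed. The protocol puts no limit on that interval.

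Doses taken meanwhile cannot be taken back. Section 10.3.2.4 warns that "vorapaxar results in residual platelet aggregation activity 4 weeks after stopping" and that there is no known antidote. Participants take vorapaxar here to test an effect on a biomarker, so tolerance for avoidable bleeding risk should be low. The point does not require the DSMB to have seen a difference between arms, only that it has recommended a hold or stop.

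**Working it through.** **Text check.** Does any section lift the 18.0 rule once the DSMB has recommended a hold after a type 2 or type 3 trigger?

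- 10.2, 10.3.2.2, 10.3.2.3 and the mandatory clause of 10.4 act on the individual who has had an event. They do not reach the others.
- The voluntary stop in 10.4 and the immediate-hazard clause in 15.2 can reach the others, but site by site and at someone's discretion. Neither is linked to a DSMB recommendation.
- 10.3.2.5 is trial-wide, but needs a fatal bleed on vorapaxar.
- 9.5 lists termination of the study as an act of the PSC. No section lets the DSMB suspend dosing.

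So the rule stands for participants without a stopping event.

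**How often a type 3 trigger might occur.** The protocol gives no figure, so this rests on assumptions. Section 3.3 reports: "Moderate or severe bleeding occurred in 4.2% of patients who received vorapaxar and 2.5% of patients who received placebo". I take these as three-year (156-week) risks with constant hazard, and GUSTO moderate or severe bleeding (10.3.2) as a rough match for BARC type 3 (Appendix 2).

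- Weekly hazard, vorapaxar: −ln(1 − 0.042)/156 = 0.000275
- Weekly hazard, placebo: −ln(1 − 0.025)/156 = 0.000162
- Expected events, 30 per arm over 12 weeks: 30 × 12 × (0.000275 + 0.000162) = 0.157
- Chance of at least one: 1 − exp(−0.157) = 14.6%; at half or double the rate, 7.6% or 27.0%

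The true rate is probably lower. Section 3.3 says 88% of those patients took aspirin and 78% a thienopyridine, and section 7.1 excludes both kinds of drug. The chance of the type 2 trigger, of a hold recommendation, and the length of any PSC delay cannot be estimated from the documents.

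**What a hold would avoid.** Assume even accrual over 26, 52 or 78 weeks, 1:1 allocation, no early stopping, and a PSC decision at a meeting within 3 working days (up to 5 calendar days).

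| | 26 weeks | 52 weeks | 78 weeks |
|---|---|---|---|
| Vorapaxar participants on drug: 30 × 12 / accrual weeks | 13.8 | 6.9 | 4.6 |
| Vorapaxar doses avoided: × 5 | 69 | 35 | 23 |

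If the trigger falls 6 weeks into accrual, the numbers on drug are 30 × 6 / accrual weeks = 6.9, 3.5 and 2.3.

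Excess weekly hazard on vorapaxar: 0.000275 − 0.000162 = 0.000113. In the largest case, the excess bleeds avoided are 13.8 × (5/7) × 0.000113 = 0.0011. At ten times the rate this is 0.011. For a 4-week delay it is 13.8 × 4 × 0.000113 = 0.006. All are conditional on a hold having been recommended.

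**What a hold would cost if the PSC lifts it.**

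- Doses lost per participant: 5/(12 × 7) = 6.0%. Section 8.0 does not extend treatment to replace them.
- Dilution, pessimistically assuming that every vorapaxar week 8 or week 12 visit during the hold or the next 7 days loses the whole effect. Visits in a 12-day window: 2 × 30 × (12/7)/accrual weeks = 3.96, 1.98, 1.32.
- Each visit counts half in the average of weeks 8 and 12 (SAP 4.1), so the contrast shrinks by visits × 0.5/30 = 6.6%, 3.3%, 2.2%. That is 0.017, 0.009 or 0.006 of the 0.26 log difference in section 6.1.

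**The case against.** The strongest reply is that section 18.0 only says a pending review does not itself interrupt treatment. A board that advises and a committee that decides is a legitimate structure, and the automatic stop for a fatal bleed suggests deliberate grading. That is fair as far as the review period goes, and dosing during the review need not change. But the sentence runs on until the PSC has acted, so it also governs the time after a hold has been recommended.

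Second, response times belong in the DSMB terms of reference, which 18.0 says are separate documents finalised before the study starts. This stands for the deadline: its absence is shown for the protocol only. It does not settle the hold, because terms of reference that suspended dosing would contradict 18.0 as written.

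Third, a deadline alone would cure an open-ended delay. A 5-day hold adds little, because the drug effect persists after stopping and participants remain exposed throughout. On expected harm this is right, and it sets the priority.

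A reader might infer that everyone keeps dosing unless a site or participant chooses otherwise. The documents do not support that: the participants with qualifying bleeds, and those with significant events attributed to vorapaxar, come off drug under 10.2, 10.3.2.2, 10.3.2.3 and 10.4. Nor do they support an inference that the PSC would be slow. The twice-yearly figure is a minimum, meetings are by teleconference as required, and each site is represented.

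**Conclusion.** The point holds in a limited form. After four type 2 events or one type 3 event, the protocol requires participants who have had no stopping event to continue study drug until the PSC acts, with no exception for a DSMB recommendation to hold or stop.

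The size is small. The chance of a type 3 trigger is about 15% on the assumptions above, probably lower in this population. With about 14 vorapaxar participants on drug, a 5-day hold avoids roughly 0.001 excess moderate or severe bleeds. Both figures rest on reading the section 3.3 percentages as three-year risks, on the rough GUSTO-to-BARC match and, for the second, on an assumed accrual period. A reader should not infer a material expected harm. The case for change is that the wording tells sites to continue against the independent board's advice, and that correcting it costs little. It is a cheap improvement of low priority.

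**What to change.** Amend section 18.0 along these lines: *During an ad hoc review recruitment is paused and randomised patients continue study treatment, except that if the DSMB recommends holding or stopping study drug, dosing in both arms is held from receipt of the recommendation until the PSC decides. The PSC is convened by teleconference within 3 working days.* Align the DSMB terms of reference, which may already set a response time. The PSC remains the decision-maker.

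The 3 working days are a suggestion, not a figure from the documents. The administrative cost is the edit and a procedure for the Project Team to notify about 7 sites. The scientific cost arises only if the PSC lifts a hold: up to about 5 of 84 doses per participant, not made up, and at most about 2% to 7% dilution of the d-dimer contrast on the pessimistic assumption.
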